### 6.4 STUDY INTERVENTION/EXPERIMENTAL MANIPULATION ADHERENCE

Adherence to the protocol will be tracked by the dashboard for the web-based intervention. User metrics will include a completion rate.

## 7 STUDY INTERVENTION/EXPERIMENTAL MANIPULATION DISCONTINUATION AND PARTICIPANT DISCONTINUATION/WITHDRAWAL

### 7.1 DISCONTINUATION OF STUDY INTERVENTION/EXPERIMENTAL MANIPULATION

When a participant discontinues from study intervention, remaining study procedures will be discontinued. Attempts will be made to collect data on the participant's reason for discontinuing participation.

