### 5.2 EXCLUSION CRITERIA

Adolescents younger than 13 years or older than 16 years at time of enrollment  
No parental consent  
Medical conditions preventing engagement in physical activity  
Medical conditions resulting in extremely restricted diets (e.g., ketogenic diet)  
Already participating in an intervention related to healthy eating, physical activity and/or obesity prevention or treatment

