##### Module 4. Motivation

- Personal: Create positive attitudes toward engagement in healthy eating and PA

- Social: Enlisting social support to increase healthy eating and PA
- Social: Identification of community resources that promote and support healthy eating and PA

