### 7.2 PARTICIPANT DISCONTINUATION/WITHDRAWAL FROM THE STUDY

Participants are free to withdraw from participation in the study at any time upon request. An investigator may discontinue a participant from the study for the following reasons:

- Significant study intervention non-compliance
- Lost-to-follow up; unable to contact subject
- The participant meets an exclusion criterion (either newly developed or not previously recognized) that precludes further study participation

The reason for participant discontinuation or withdrawal from the study will be recorded.

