### 7.3 LOST TO FOLLOW-UP

A participant will be considered lost to follow-up if he or she fails to complete the intervention or posttest and follow-up assessments and study staff are unable to contact the participant after at least 2 attempts.

The following actions must be taken if a participant fails to complete the intervention modules or assessments:

- The site will attempt to contact the participant and ascertain if the participant wishes to and/or should continue in the study
- Before a participant is deemed lost to follow-up, the investigator or designee will make every effort to regain contact with the participant (where possible, 3 text messages and/or emails). These contact attempts will be documented in the participant's study file.
- Should the participant continue to be unreachable, he or she will be considered to have withdrawn from the study with a primary reason of lost to follow-up.

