### 9.3 POPULATIONS FOR ANALYSES

Intention-to-Treat (ITT) analysis population (i.e., all randomized participants).

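### Section 7.1 ends outcome collection when a participant discontinues the intervention, so the ITT analysis promised in 9.3 becomes, as written, a comparison of those who stayed on

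*Combined protocol and SAP*

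**What the plan says.** - **Section 7.1:** "When a participant discontinues from study intervention, remaining study procedures will be discontinued". No exception is given; the only further step is to try to learn the reason. The Schedule of Activities (1.2) shows what remains after the modules: the posttest survey in week 8 and the 1-month follow-up survey in week 12.
- **Section 7.2:** "An investigator may discontinue a participant from the study for the following reasons". The list includes "Significant study intervention non-compliance" and "The participant meets an exclusion criterion (either newly developed or not previously recognized) that precludes further study participation". These end participation in the study, not only in the modules. No threshold for non-compliance is given, and 6.3 says masking does not apply.
- **Section 7.3:** a participant may be classed as lost to follow-up who "fails to complete the intervention or posttest and follow-up assessments", provided that staff also cannot reach them after at least two attempts.
- **Section 9.3:** the analysis set is the "Intention-to-Treat (ITT) analysis population (i.e., all randomized participants").
- **Section 9.4.1:** change from pretest to 1-month follow-up is compared by t-test, and improved versus not improved by chi-square test. Group differences and SDs of change then feed the sample size of the next study. No method for missing outcomes and no sensitivity analysis is described.

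**The concern.** An intention-to-treat analysis needs outcomes from participants whatever their adherence. Sections 7.1 and 7.2 tie outcome collection to adherence, so the outcomes of discontinuers are missing by rule and not only by chance. A change score cannot be computed without a 1-month value, and nothing in the plan supplies one.

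Two things are at stake. First, Module 2 differs between arms (health literacy versus vaping), so stopping may differ between arms. Removal for non-compliance is also a judgement made without masking. Either could leave groups that are no longer comparable. Second, the pilot exists to supply estimates for a full-scale trial (4.2 and 9.4.1). An effect estimated in those who stayed on may be larger than the effect in everyone randomised, and the next trial would then be too small.

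**Working it through.** **No figure to reproduce.** Section 9.2 says the sample size did not come from a power calculation, and the plan states no N, SD, alpha, effect size or dropout rate. The conflict is shown by reading the sections together; the numbers below are illustrations on assumed inputs.

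**The sections side by side**
1. 9.3 requires everyone randomised to be in the analysis.
2. 9.4.1 requires a pretest and a 1-month value from each of them.
3. 7.1 stops collection of the 1-month value once the intervention is discontinued, and 7.2 permits the same result for non-compliance.
4. No section provides for later assessment or for a replacement value. The t-test therefore runs only on those with a week-12 survey.

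**Bias in the contrast.** Let d be the share who stop in an arm and g the gap in mean change, completers minus stoppers, in SD units. The arm mean over everyone is (1 − d) × completer mean + d × stopper mean, so the completer mean exceeds it by d × g. With the same g in both arms, the bias in the contrast is g × (dE − dC).
- 30% vs 20%, g = 0.5: 0.5 × 0.10 = 0.05 SD.
- 40% vs 20%, g = 0.5: 0.5 × 0.20 = 0.10 SD.
- For g from 0.3 to 0.8: 0.03 to 0.08 SD at 20% vs 10%, and 0.06 to 0.16 SD at 30% vs 10% or 40% vs 20%.
- Equal stopping and equal g: 0.

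**Precision.** Losing a share a of outcomes multiplies the standard error by 1/√(1 − a): 1.118 at 20%, 1.195 at 30% and 1.291 at 40%. That is 12% to 29% wider over the range. It is an upper limit on the cost of the rule, because some stoppers would not return a survey even if asked.

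**Effect on the next trial.** Assume completers show 0.30 SD and stoppers in the experimental arm gain nothing relative to control. The gap now differs by arm, so the estimate is distorted even when stopping is equal. The effect in everyone randomised is 0.30 × (1 − d). With two-sided alpha 0.05 and 80% power, n per arm = 2 × (1.96 + 0.84)² / effect², which is 175 for 0.30 SD.

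| Stopping | Effect in all randomised (SD) | n per arm needed | Power with 175 per arm |
|---|---|---|---|
| 10% | 0.27 | 216 | 71% |
| 20% | 0.24 | 273 | 61% |
| 30% | 0.21 | 356 | 50% |
| 40% | 0.18 | 485 | 39% |

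**The case against.** The strongest reply is that 7.1 concerns formal discontinuation, not a participant who has merely fallen behind. Modules are self-paced (6.1.2), and the sentence after the rule in 7.1 speaks of leaving participation altogether. For those who do not finish, 7.3 has staff ask whether the participant wishes to, or should, continue. This stands in part: a stalled participant is not cut off automatically. But no section says when stalling becomes discontinuation or that surveys continue afterwards, and 7.2 makes non-compliance a ground for removal from the study.

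It can also be said that this is an unpowered feasibility pilot with reminders, points and bonus incentives for retention (5.4), and that any loss is of unknown size. That is fair as to magnitude. It does not remove the conflict, and the estimates are meant for reuse.

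A reader might go further than the documents allow in four ways:
- **That ITT is impossible.** Pretest is taken before the interventions start, so imputation or bounds could cover everyone. What is lacking is observed outcomes and any stated method.
- **That newly meeting an exclusion criterion ends follow-up automatically.** Section 7.2 says the investigator may act, and only where the criterion precludes participation.
- **That good responders are removed for responding.** Module 4 includes "Social: Identification of community resources that promote and support healthy eating and PA", and 5.2 excludes those "Already participating in an intervention related to healthy eating, physical activity and/or obesity prevention or treatment". Finding a resource is not joining an intervention, and the criterion reads most naturally as a status at enrolment. Module 4 is the same in both arms, and nothing shows that uptake or enforcement would differ.
- **That missing modules alone make a participant lost to follow-up.** Section 7.3 also requires failed contact.

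**Conclusion.** The conflict between 7.1 and 7.2 on one side and 9.3 and 9.4.1 on the other is real and follows from the text alone. Followed literally, the plan reports a comparison of participants who stayed on under an ITT label and carries it into the design of the next trial.

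Dependence of the losses on adherence follows directly from the rules. Dependence on outcome is an inference: a reasonable one, but not shown. The size cannot be derived from the documents. The 0.05 to 0.10 SD bias rests on an assumed 10 or 20 percentage-point difference in stopping and an assumed 0.5 SD gap. If stopping is low and both stopping and the gap are equal across arms, the bias is negligible. The table for the next trial rests on its own assumption that stoppers gain nothing.

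The point deserves correction before data collection because outcomes that were never collected cannot be recovered at analysis.

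**What to change.** The change concerns data collection and analysis only.

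- **7.1:** separate stopping the modules from leaving the study. Keep sending the posttest and 1-month surveys to every randomised participant, on dates counted from randomisation (weeks 8 and 12 of the schedule, so 6 and 10 weeks after the week-2 randomisation), unless permission or assent for data collection is withdrawn.
- **7.2:** state that non-compliance, or a newly met exclusion criterion, does not by itself end survey collection, and reconcile the section with 9.3. Any decision on stopping the intervention stays with the investigator. This point does not ask for a change to the 5.2 criteria or to when they apply, since they include medical conditions.
- **7.3:** base loss to follow-up on missing surveys together with failed contact, not on missing modules.
- **9.4.1:** analyse all randomised participants, name the method for outcomes still missing (for example a likelihood-based model using pretest, posttest and 1-month values, or multiple imputation), cover the binary outcomes too, and add a sensitivity analysis in which the missing outcomes are assumed worse than the observed ones. Continued surveys will not remove ordinary non-response, so this step is needed as well.

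Cost: wording in four sections, some additional analysis, and a few extra gift cards and reminders. The outcome surveys are already electronic (10.1.7.1), and the reminder and incentive system already exists (5.4).

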### 7.2 PARTICIPANT DISCONTINUATION/WITHDRAWAL FROM THE STUDY

Participants are free to withdraw from participation in the study at any time upon request. An investigator may discontinue a participant from the study for the following reasons:

- Significant study intervention non-compliance
- Lost-to-follow up; unable to contact subject
- The participant meets an exclusion criterion (either newly developed or not previously recognized) that precludes further study participation

The reason for participant discontinuation or withdrawal from the study will be recorded.

### 7.3 LOST TO FOLLOW-UP

A participant will be considered lost to follow-up if he or she fails to complete the intervention or posttest and follow-up assessments and study staff are unable to contact the participant after at least 2 attempts.

The following actions must be taken if a participant fails to complete the intervention modules or assessments:

- The site will attempt to contact the participant and ascertain if the participant wishes to and/or should continue in the study
- Before a participant is deemed lost to follow-up, the investigator or designee will make every effort to regain contact with the participant (where possible, 3 text messages and/or emails). These contact attempts will be documented in the participant's study file.
- Should the participant continue to be unreachable, he or she will be considered to have withdrawn from the study with a primary reason of lost to follow-up.

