#### Retention

One of the advantages of a digital intervention is that it decreases the travel and time burdens as individuals may complete the modules based on their individual schedules. While adolescents may not prioritize the intervention or forget about it given the lack of deadline, the intervention will have a built-in point system to immediately incentivize data collection and module completion. For example, participants will be provided with a suggested schedule for completing the modules and will receive email and text prompts encouraging them to log in and complete the module prior to the scheduled date. They will be incentivized through the point system for completing the module early and according

to the schedule. Participants will also be incentivized through the point system to complete each module in one sitting to facilitate making connections across the module. Though participants will receive gift cards at each data collection completion, they will also receive points for completing data collections. These points may be redeemed for prizes at the end of the study through the points store where more desirable prizes will require more points. Collecting biometric data at posttest and follow-up may be difficult given that all other data collection will occur online. Bonus incentives for completing all aspects of the study (intervention and all data collection) should further motivate participants to maintain involvement in the project. The use of email and text prompts throughout the study should also encourage retention. We plan to collect multiple phone numbers and email address for participants and their parents to be able to reach them in the event of lost devices or changes in phone numbers or email addresses.

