### 6.3 MEASURES TO MINIMIZE BIAS: RANDOMIZATION AND BLINDING

Masking is not applicable to the study design. Participants will be randomized to conditions upon enrollment with the goal of balancing the number of participants in each condition (e.g., 1st participant assigned to condition 1, 2nd to condition 2, 3rd to condition 1).

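### Section 7.3 can be read to class slow, unresponsive participants as lost to follow-up and withdrawn before the Week 12 primary survey is due

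*Combined protocol and SAP*

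**What the plan says.** Section 7.3 sets two conditions for lost to follow-up. The participant "fails to complete the intervention or posttest and follow-up assessments", and "study staff are unable to contact the participant after at least 2 attempts". An action list follows for anyone who does not finish the modules or the assessments. The site makes contact to "ascertain if the participant wishes to and/or should continue in the study". Before the status is given, staff are to do all they can to regain contact ("where possible, 3 text messages and/or emails") and to document the attempts. If the participant still cannot be reached, "he or she will be considered to have withdrawn from the study with a primary reason of lost to follow-up".

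Other parts of the protocol that bear on this:

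- Section 1.2 places the modules in Weeks 3-7, the posttest at Week 8 and the 1-month follow-up at Week 12. The synopsis names the 1-month follow-up as the primary endpoint.
- Section 6.1.2 lets participants work through the modules when it suits them, on a suggested schedule. The Retention text of section 5.4 acknowledges that there is no deadline.
- The same Retention text states: "We plan to collect multiple phone numbers and email address for participants and their parents to be able to reach them".
- Section 7.1 ends remaining study procedures when a participant stops the intervention. Section 7.2 lets the investigator discontinue a participant for significant non-compliance or for loss to follow-up.
- Section 9.3 names the "Intention-to-Treat (ITT) analysis population (i.e., all randomized participants". Section 9.4.1 compares change from pretest to 1-month follow-up by t-test and gives no method for missing values.
- On masking, section 6.3 says: "Masking is not applicable to the study design".

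**The concern.** Lost to follow-up should describe a participant whose outcome could not be obtained. Here the status can also rest on unfinished modules, which is a matter of adherence, and it leads to withdrawal. The protocol never says when a participant has failed to complete modules that have no deadline. Staff could therefore reach that judgement in Weeks 3-8, before the Week 12 survey exists to be missed.

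Those closed out this way would be the least engaged participants. Their behavior change may differ from that of the others, and the two arms differ in one module, so engagement need not be equal between them. The primary comparison needs a Week 12 value, so an early close-out leaves a randomized participant with no primary outcome. Section 9.4.1 also uses the observed changes and their standard deviations to size the next study, so any selection would carry forward into that calculation.

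**Working it through.** The plan gives no sample size, attrition rate or reply rate, so there is no figure to reproduce. The main check is textual.

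**Step 1: can the status precede Week 12?** The non-completion condition joins its terms with both an or and an and. Read as the intervention, or else the two assessments, unfinished modules are enough. Read as the intervention or posttest, together with the follow-up, the Week 12 survey must already have been missed. The action list favors the first reading: it starts when modules or assessments are incomplete, and it ends in withdrawal. Nothing in section 7.3 ties the status to the Week 12 date.

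**Step 2: what contact is needed?** Failed contact is required as well. Two attempts are the floor and three messages are a target where possible. Channels beyond text and email, spacing and time window are not stated, and parent contacts are neither required nor excluded.

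**Step 3: what follows?** Section 7.3 says the participant will be considered withdrawn, while section 7.2 says the investigator may discontinue for the same reason. Neither says outright that the Week 12 survey is then withheld; that follows from the ordinary meaning of withdrawal.

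**Step 4: what does the analysis need?** All randomized participants (9.3) and the 1-month value (9.4.1). Early withdrawal removes the second for some of the first.

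**Illustration on assumed rates.** Let u be the share with unfinished modules by Week 8, p the chance that one attempt gets a reply, k the number of independent attempts, and w the share of those closed out who would have answered at Week 12.

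Closed out early = u × (1 − p)^k. Avoidable loss = u × (1 − p)^k × w.

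With u = 0.25 and w = 0.3 to 0.5, all assumed, as percentages of randomized participants:

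| p | Closed early, k = 2 | Closed early, k = 3 | Avoidable loss, k = 2 | Avoidable loss, k = 3 |
|---|---|---|---|---|
| 0.2 | 16.0 | 12.8 | 4.8 to 8.0 | 3.8 to 6.4 |
| 0.3 | 12.3 | 8.6 | 3.7 to 6.1 | 2.6 to 4.3 |
| 0.4 | 9.0 | 5.4 | 2.7 to 4.5 | 1.6 to 2.7 |
| 0.5 | 6.3 | 3.1 | 1.9 to 3.1 | 0.9 to 1.6 |
| 0.7 | 2.3 | 0.7 | 0.7 to 1.1 | 0.2 to 0.3 |

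For example, p = 0.2 and k = 2 give 0.25 × 0.64 = 0.160, and 0.160 × 0.5 = 0.080. The results scale in proportion to u and w.

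**The case against.** The strongest reply is that section 7.3 already protects participants. Non-completion alone is not enough, because staff must also have failed to make contact. The three-message step comes before the status is assigned, so two missed messages would not normally close anyone out. The wording about making every effort leaves room to use the parent contacts. One reading of the non-completion condition delays the status until Week 12 has been missed. And this is a feasibility pilot with no power calculation.

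Much of this stands, and it rules out several stronger readings that a reader might infer:

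- *That staff can close out reachable participants under the lost-to-follow-up rule.* They cannot: someone who answers does not meet the definition. The accurate description is a participant who missed two or three messages and might have replied later or by another channel. Participants who are in contact can leave follow-up through sections 7.1 and 7.2, and possibly through the site's undefined judgement in 7.3 on whether a participant should continue.
- *That the protocol holds rival contact rules.* Two is a floor and three a soft target. Section 5.4 sets no threshold at all; it only says that contact details are collected.
- *That contact effort differs by arm.* Lack of masking makes this possible, but no passage shows it. Attempts must be documented, and the prompts are described without distinction by arm.

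What the reply does not remove is the timing. A third message delays the status by one message, not until Week 12. The favorable reading of the non-completion condition is available but is not the one the action list supports. Pilot status lowers the stakes for a significance test, but the pilot's changes and standard deviations are meant to size the next trial.

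**Conclusion.** The point holds as a problem of definition and timing. On the natural reading of section 7.3, unfinished modules plus failed contact can lead to withdrawal before the primary survey is due. That sits badly with an analysis of all randomized participants on change to 1 month. The text is ambiguous, so this is something the plan permits rather than something it directs.

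The documents do not fix the size. On the assumed rates above, avoidable loss of primary data runs from about 0.2% to 8% of randomized participants. The conclusion rests on two inferences: that module non-completion alone satisfies the non-completion condition, and that a participant considered withdrawn is not sent the Week 12 survey. The choice between two and three attempts is secondary. The change is worth making because it is cheap and limits missing data related to engagement.

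**What to change.** In section 7.3:

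1. Remove non-completion of the intervention from the definition of lost to follow-up. Record it as adherence under section 6.4.
2. Assign the status only after the Week 12 survey has been sent and the documented contact attempts for that survey have failed.
3. Until then, send the Week 8 and Week 12 surveys to every randomized participant who has not withdrawn permission or assent, whatever their module completion.
4. State one minimum number of contact attempts, the same in both arms, and say that the parent contacts collected under section 5.4 may be used. The exact number is an operational choice.

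Sections 7.1 and 7.2 must be reconciled with this rule and with section 9.3 in the same amendment. As written, 7.1 ends remaining procedures when the intervention stops and 7.2 allows discontinuation for non-compliance, so a change to 7.3 alone would create a new conflict. What has to be settled there is whether outcome surveys continue.

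The cost is rewording in section 7, a few more electronic messages per non-responder, some staff time, and later closing of non-responders. Surveys are already electronic, prompts already go out by email and text, and gift cards for data collection are already planned.
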